Each morning during the eight-week intervention, participants will receive questions about their current affect, intent to engage in physical activity, and self-efficacy for engaging in physical activity. At each request, participants will be given the option to “snooze” the request for up to one hour. The assessment questions will be viewed and responded to on the Fitbit Versa device. We will utilize the Fitbase Engage platform (see Figure 3), which utilizes the Fitbit SDK to deliver assessments and message prompts via the Fitbit Versa. Assessment questions have been validated for their use in EMA.⁵⁻⁷ Daily questions will include:

Figure 3. Representations of messages delivered via the Fitbase Engage platform.

*Actual messages will be customized as described below.

Physical Activity Intention (One item; 1 strongly disagree to 5 strongly agree)

“I intend to meet my goal of XXX steps today”

Physical Activity Self-Efficacy (One item; 1 not confident at all to 5 completely confident)

“I believe I can complete my goal of XXX steps today.”

Affect (Nine items assessing positive and negative affect; 1 not at all to 5 extremely)

“How (happy, cheerful, relaxed, stressed, anxious, angry, depressed, energetic, fatigued/tired) do you feel right now?”

Affective Framing Messages. After completing the daily EMAs, participants may receive an affective framing message. Message delivery will occur on a 1:1 randomization schedule, such that participants will receive messages on 28 of the 56 intervention days. The study biostatistician will generate randomization schedules for each participant using block randomization with variable block sizes. Messages will be randomly selected from a pool of 14 messages, meaning each message will be received twice during the eight-week study. Messages will emphasize potential improvements in mood, energy, and calmness.^{8,9} Examples of these messages:

“Research has shown that physical activity often results in improved mood.”

“Most people report feeling happier and more relaxed after exercise.”

Weekly Goal Setting. Each Sunday evening, participants will receive a prompt to select a step goal for the upcoming week. Along with this prompt, participants will receive feedback on their activity during the previous week. Participants will receive either: 1) the average daily number of steps taken during the previous week, or 2) the highest daily number of steps taken during the previous week.

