A repeated-measures mixed effects model will be used as described in Klasnja et al. (2015) with participant and time as random effects and other effects as fixed. Daily step count will be the dependent variable while main effects of affective framing intervention (message/no message) and linear time effects will be within-subjects factors, and an intervention by time interaction term will be included. We also will consider more complex effects of time (e.g., quadratic effects). We will include scores of the Physical Activity Intention, Physical Activity Self-Efficacy, and Affect as time-varying covariates. As described in Klasnja, et al. (2015) we will include the scores for the day prior to the intervention so the covariates will not be affected by the intervention. We will also classify each day as a cancer treatment day (i.e. day on which chemotherapy or radiation therapy is received) or not and presence/absence of cancer treatment will also be a time-varying covariate. A time lag is not needed for this covariate as the timing of cancer treatment will not be influenced by the intervention. Presence/absence of an implementation planning message on each day will also be included as a time-varying covariate and an affective framing by planning message interaction will be included to assess synergistic effects of the two messages. The baseline measurement of theoretical moderators of physical activity behavior change (Physical Activity Stage of Change, Physical Activity Self-Efficacy, Multidimensional Outcome Expectations for Exercise Scale) and psychosocial characteristics Functional Assessment of Cancer Therapy – General, Quick Inventory of Depressive Symptomatology – Self-Rated, Brief Fatigue Inventory) will be considered as covariates as will other baseline demographic and clinical variables determined to improve the fit of the final model.

Hypothesis 2b: *Participants will have greater daily step counts on days receiving the implementation planning message compared to non-message days.*

The same repeated-measures mixed effects model described for Hypothesis 2a will be used for this hypothesis. Only the interpretation of the results will be different as the presence/absence of the implementation message will be the main effect and the affective framing intervention will be considered the covariate.

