Hypothesis 2c: Participants randomized to receive feedback prompts reporting their highest daily step count will achieve greater step counts compared to participants that receive feedback prompts reporting their average daily step counts.

Participants will be randomized at baseline for the duration of the study because we expect that the intervention will have a cumulative effect over the course of the study. The hypothesis will be tested using a repeated-measures mixed effects model with participant and time as random effects and other effects as fixed. Daily step count will be the dependent variable. The intervention (highest vs average steps feedback) will be a between-subjects factor and time the within-subjects factor and an intervention by time interaction term will be included. We also will consider more complex effects of time (e.g., quadratic effects). The baseline characteristics described in Hypothesis 2a will be considered to improve the fit of the final model. We will also consider the inclusion of time-varying covariates if a clinically meaningful imbalance between groups is found.

Exploratory analyses

For Aim 2a and 2b we will also evaluate the moderating effects of time-varying factors measured through daily EMA (Physical Activity Intention, Physical Activity Self-Efficacy, and Affect). Our ultimate goal is to be able to evaluate these factors to inform decision rules in the ultimate adaptable intervention. The proposed sample size limits the power to detect time-varying moderators of intervention effects and formal analysis of moderating effects will only be conducted in the subsequent clinical trial. These analyses will use a repeated-measures mixed effects model as described above for Hypotheses 2a and 2b, and the moderating effect will be represented by a 3-way interaction of intervention, covariate, and time.

Power calculations

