The study design for Aims 2a and 2b will require subjects to be randomized each day to receive the intervention or not. Each day there will be a 50% probability of receiving the intervention (1:1 randomization schedule) so that the average subject will receive the intervention on 28 of the 56 study days. The sample size for Hypotheses 2a and 2b of 50 is based on the sample sizes in the table below which assume 80% power with an alpha=0.05. We also assume that the effect size (standardized difference between treatment groups, similar to Cohen's d) is constant during the 56-day study period. Note that for Cohen's d an effect size of 0.2 or less is considered 'small' (Cohen, 1998) (small effect=0.2, medium effect=0.5, large effect=0.8), therefore, the proposed sample size of 50 will be able to detect effect sizes that are about half of a 'small' effect.

The power analysis for Hypothesis 2c is based on a repeated measures analysis of variance comparison of two groups with 56 repeated observations assuming a correlation between repeated measurements of 0.5, 80% power, and alpha=0.05. Given these assumptions, an effect size of 0.29 can be detected with the proposed sample size of 50. Based on Cohen's guidelines for an ANOVA f-test an effect size of 0.29 is slightly larger than a 'medium' effect (small effect=0.1, medium effect=0.25, large effect=0.4).

Table 1. Sample size calculations.

Hypotheses 2a and 2b		Hypothesis 2c	
Effect Size	Sample Size to Obtain 80% Power	Effect Size	Sample Size to Obtain 80% Power
0.200	17	0.290	50
0.109	50	0.265	60
0.099	60	0.245	70
0.091	70	0.203	100
0.076	100	0.100	402

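### Hypothesis 2c counts the days before the first Sunday feedback as outcome days and names no pre-feedback step count as a baseline covariate

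*Combined protocol and SAP*

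**What the plan says.** Section 5.4 (Weekly Goal Setting) describes the intervention: "Each Sunday evening, participants will receive a prompt to select a step goal for the upcoming week". Feedback on the previous week comes with that prompt. One arm gets this version: "Participants will receive either: 1) the average daily number of steps taken during the previous week". The other arm gets the highest daily count instead. Section 5.4 describes no run-in, and the start weekday is not stated.

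Section 7.0, Hypothesis 2c, randomizes participants at baseline for the whole study, on the ground that "we expect that the intervention will have a cumulative effect over the course of the study". The outcome definition excludes no days: "Daily step count will be the dependent variable". The model has arm, time and arm-by-time terms, and the text does not say which of them tests 2c. On baseline adjustment it says: "The baseline characteristics described in Hypothesis 2a will be considered to improve the fit of the final model".

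Under Hypothesis 2a those characteristics are stage of change, self-efficacy, outcome expectations, FACT-G, QIDS-SR and BFI, followed by an open clause: "as will other baseline demographic and clinical variables determined to improve the fit of the final model".

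The power calculation for 2c is a "comparison of two groups with 56 repeated observations assuming a correlation between repeated measurements of 0.5". It gives a detectable f of 0.29 at N = 50.

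**The concern.** The two arms differ only in the figure shown on Sunday evening, so they cannot differ through the intervention before the first prompt. Those days (1 to 7 if the first Sunday counts) carry no arm effect. Treating them as outcome days dilutes a constant effect. It also leaves unused the one measurement that best predicts a participant's later step count.

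This matters most for 2c because it is the plan's only between-person comparison and its least sensitive one. A between-subjects contrast carries the full person-to-person variance. The participant random effect models that variance but does not remove it from the arm contrast. The Background section says that efficacy results will decide which components enter the adaptive intervention, so an imprecise 2c result could lead to a useful component being dropped.

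**Working it through.** **Inputs.** From Section 7.0, Power calculations: N = 50, 56 observations, ρ = 0.5, α = 0.05, 80% power, f = 0.29. Assumed: equal arms (25 and 25), and k = 1 to 7 pre-feedback days. Effects are in units of the daily-step SD (variance 1), and for two equal arms f = d/2.

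**Step 1: the plan's figure.** The variance of a mean of m days is V(m) = ρ + (1 − ρ)/m.

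- V(56) = 0.5 + 0.5/56 = 0.509.
- SE of the arm difference = √(4 × 0.509/50) = 0.202.
- With 48 df (noncentral F), f = 0.29 gives power 0.804, and 80% power needs f = 0.288. The stated 0.29 reproduces.
- Of the 0.509, 0.500 (98%) is stable person-to-person difference.

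**Step 2: dilution.** If the effect is zero for k days, the 56-day contrast shrinks by k/56: 1/56 = 1.8% to 7/56 = 12.5%.

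**Step 3: adjustment.** Use the 56 − k later days as outcome and the mean of the k earlier days as covariate. The residual variance is v = V(56 − k) − ρ²/V(k).

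- k = 1: 0.509 − 0.25/1.000 = 0.259
- k = 4: 0.510 − 0.25/0.625 = 0.110
- k = 7: 0.510 − 0.25/0.571 = 0.073

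The table uses SE = √(4v/50), with 48 df for the planned analysis and 47 adjusted. The power columns are for a constant 0.3 SD difference after the first prompt (f = 0.15). The arm-by-time column uses a normal approximation.

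| Pre-feedback days | Adjusted SE | Detectable f, adjusted | Power, planned arm term | Power, planned arm-by-time | Power, adjusted arm term |
|---|---|---|---|---|---|
| 1 | 0.144 | 0.206 | 30% | 6% | 53% |
| 4 | 0.094 | 0.134 | 27% | 25% | 88% |
| 7 | 0.076 | 0.109 | 25% | 57% | 97% |

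**Step 4: mixed start weekdays** (uniform, assumed), same effect.

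- Planned arm term: SE 0.202, power 27%.
- Covariate adjustment: SE 0.108, power 78%.
- All-days mixed model with a common post-prompt term: SE 0.097, power 86%.

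**Step 5: less favourable settings, k = 7.**

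- Random slopes with SD 0.4 over 56 days (assumed): f goes from 0.30 to 0.14.
- Part-stable, part-decaying correlation (intercept share 0.25 plus AR(1) share 0.25, φ = 0.9): f goes from 0.232 to 0.173, variance 44% lower.
- All correlation decaying: variance 28% lower (share 0.6, φ = 0.97) or 11% lower (share 0.53, φ = 0.95).
- Effect growing linearly and averaging 0.3 SD: the planned arm-by-time test already has about 100% power.

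**Step 6: does the remedy hold its error rate?** Both arms receive a goal prompt and feedback on the first Sunday, so a change shared by both is plausible. The check used no true arm effect and a shared change of 0.2 SD at that point.

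- Arm indicator set to 0 before the prompt, without a common before/after term: spurious effects of 0.13, 0.16 and 0.15 SD and rejection rates of 19%, 57% and 68% at k = 1, 4 and 7.
- Same model with the common term: 0.00 SD and 5.0%.
- Covariate adjustment (6,000 simulations): 4.9%, 5.3% and 4.6% at k = 1, 4 and 7, and 4.9% with mixed k.

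**The case against.** Nothing in the plan is wrong: assignment is randomized, the comparison is unbiased, and 0.29 is arithmetically correct. If 0.29 is read as the 56-day average effect, the stated power stands without dilution. All of that is right, and the point is one of efficiency.

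The stronger objection is that the plan expects a cumulative effect and includes arm-by-time, which already detects a linearly growing effect. It also gains from the early days when the effect is constant: with 7 pre-feedback days its power is about 57%, so setting 25% against 97% overstates the contrast. This stands in part. However, the plan does not name arm-by-time as the test of 2c, and its power calculation is for the two-group comparison. For a constant effect, arm-by-time stays below the adjusted arm term at every k.

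Constant correlation is also a simplification. It is the plan's own, but the gain shrinks if correlation decays, to as little as an 11% variance cut in the cases examined.

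The number of pre-feedback days is an assumption. The daily question refers to a step goal throughout, and how the first goal is set is not described. If feedback waits for a full previous week, the period could exceed 7 days.

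Finally, some participants may have no valid pre-prompt day. If 30% of days were invalid independently (matching the 70% wear benchmark) and start weekdays were uniform, that would be about 6%, or 3 of 50. A pure covariate adjustment needs a rule for them; the all-days model keeps them.

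The open clause on clinical variables might admit a step count, but choosing covariates by fit is weaker than naming the strongest one in advance.

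**Conclusion.** The concern holds as a recommended improvement in efficiency; it is not an error in validity. The 2c model treats days without any arm difference as outcome days and names no pre-feedback step count. Under the plan's own ρ = 0.5, with equal arms and a constant effect, using those days as baseline cuts the variance of the arm contrast by a factor of 2.0 (0.509/0.259), 4.6 (0.509/0.110) or 7.0 (0.509/0.073) for 1, 4 or 7 days. The gain is moderate under mixed correlation and small if all correlation decays. For a linearly growing effect, the planned arm-by-time term already does the work. Confidence in the size is medium, because the start weekday and the true correlation pattern are not given.

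**What to change.** Prespecify one of two models for 2c:

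1. Use as outcome only the days after each participant's first Sunday prompt, and adjust for that participant's mean daily steps before it. Keep the participant random effect and the arm-by-time term.
2. Keep all days, code the arm indicator 0 for everyone before the first prompt, and add a before/after-first-prompt term common to both arms. Do not use the recoded indicator without that common term.

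Option 2 is somewhat more precise when start weekdays differ, and it keeps participants with no valid pre-prompt day. Option 1 needs a minimum number of valid-wear days and a rule for participants below it.

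In either model, centre time within the post-prompt days so that the arm term is the average post-prompt difference. In the covariate-adjusted model, adding the centred arm-by-time term leaves the arm SE unchanged (0.144, 0.094 and 0.076 at k = 1, 4 and 7). State whether the arm term or arm-by-time tests 2c.

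The cost is SAP wording, using Fitbit data already collected, with no extra participants or visits. Under option 1, up to 7 outcome days per participant become baseline days, which moves the variance of the outcome mean only from 0.509 to 0.510.

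### Hypothesis 2c: fit-driven choice of covariates from an open-ended list can raise the type I error of the average arm difference to about 7-10%, and adjusting for daily ratings because the arms differ can remove part of the effect

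*Combined protocol and SAP*

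**What the plan says.** All of this is in Section 7.0 of the combined protocol and SAP.

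- **Design.** "Participants will be randomized at baseline for the duration of the study", and "The intervention (highest vs average steps feedback) will be a between-subjects factor". The model also has an arm-by-time interaction, with participant and time as random effects. The arms are expected to diverge cumulatively.
- **Baseline covariates.** "The baseline characteristics described in Hypothesis 2a will be considered to improve the fit of the final model". Hypothesis 2a defines that pool: three theoretical-moderator scales, three psychosocial scales and "other baseline demographic and clinical variables determined to improve the fit of the final model". There is no closed list, criterion, threshold or order, and nothing on whether the arm term is present during selection.
- **Time-varying covariates.** "We will also consider the inclusion of time-varying covariates if a clinically meaningful imbalance between groups is found". The 2c text does not name them. Those defined under 2a are the daily intention, self-efficacy and affect ratings, cancer-treatment day, and the indicator for the other message.
- **Error rate.** The 2c power paragraph works at a 5% alpha and 80% power. No allowance for selection is stated.

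**The concern.** Two things could go wrong with the 2c test.

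First, the arm effect rests on 50 people, however many days each contributes. If many covariates are screened on the same outcome and the final model is then tested as though it had been fixed in advance, the residual error is understated and the test can reject too often. The within-person contrasts 2a and 2b are much less exposed, because a baseline covariate is constant within a person and says little about that person's message days against other days.

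Secondly, a covariate measured after randomisation and added because the arms differ on it may be part of how the feedback works. Adjusting for it can take away some of the effect that 2c is meant to detect.

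**Working it through.** **1. The plan's own 2c figure.** The basis is "a repeated measures analysis of variance comparison of two groups with 56 repeated observations". The plan takes 0.5 for the correlation between days, a 5% alpha and 80% power. For a between-person factor, with f = 0.29, N = 50, m = 56 and ρ = 0.5:

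λ = f²·N·m / [1 + (m − 1)ρ] = 0.0841 × 2,800 / 28.5 = 8.26, on 1 and 48 degrees of freedom.

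This gives power 0.804, which agrees with the statement that "an effect size of 0.29 can be detected with the proposed sample size of 50". The other four 2c rows of the sample-size table (60, 70, 100 and 402) also reproduce.

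**2. Why people, not days, are the unit.** In units of the daily variance, a 56-day mean has variance 28.5/56 = 0.509. With unlimited days it would still be 0.5. The between-person part dominates.

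**3. Number of candidates.** The 2a text names 6 scales. The schedule in Section 6.1 adds 5 items (age, gender, race, diagnosis, stage) and 3 more (weight, height, ECOG): 6 + 5 + 3 = 14. Only the six are named as candidates. The count of 14 is an inference from what is collected.

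**4. Simulated type I error.** Null trials were run on participant means, which for balanced data is equivalent to the random-intercept test of the arm effect.

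- Assumed: 25 per arm (the plan states no ratio); candidates correlated 0.3 with one another and explaining 0% or 30% of between-person variance; final two-sided t test at 5% with between-person degrees of freedom.
- Size: 8,000 trials per setting (4,000 for 30 candidates). The simulation standard error at a true 9% is √(0.09 × 0.91/8,000) = 0.32 points.

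| Candidates | Selection rule, arm in the model | Type I error |
|---|---|---|
| 6 | all rules tried | 5.3-6.4% |
| 10 | AIC | 7.4-8.0% |
| 10 | p<0.05 | 6.2-7.7% |
| 14 | AIC or p<0.20 | 8.8-9.7% |
| 14 | p<0.05 | 6.9-8.1% |
| 14 | BIC, n = 50 | 7.1-7.9% |
| 14 | BIC, n = 2,800 | 5.7-7.0% |
| 20 | all rules tried | 5.4-12.7% |
| 30 | all rules tried | 5.9-21% |
| any | selection without the arm | 4.5-5.4% |
| any | all candidates as a fixed set | 4.5-5.7% |

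A separate forward-AIC simulation with the arm in the model gave 6.4-6.5% for 6 candidates, 7.0-7.6% for 10 and 8.0-8.6% for 14. It gave 4.6-5.0% with the arm omitted and 4.5-5.6% with a fixed list.

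The contrast between the rules has a simple explanation. Under the null, the arm labels are independent of outcomes and baseline covariates, so a selection that never sees the labels leaves the test essentially undisturbed. A selection made with the arm in the model depends on the labels.

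**5. The arm-by-time term.** A further simulation (2,000 null trials per setting, forward AIC with the arm in the model, baseline covariates as main effects) gave 4.3-4.9% for arm-by-time with 14 candidates, against 8.3-9.4% for the mean contrast in the same runs.

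**6. Time-varying covariates.** No arithmetic applies; the passages are set side by side.

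- Under 2a, the daily ratings enter with a one-day lag, so that they precede that day's message.
- Under 2c, the arm is fixed from baseline and feedback arrives every Sunday evening (Section 5.4). After the first prompt, yesterday's rating is already post-feedback, so the lag gives no protection.
- The intention and self-efficacy items ask about the participant's step goal, which is chosen at the same prompt that delivers the feedback (Section 5.4). They are plausible steps on the path from feedback to steps walked.
- Cancer-treatment day differs: the 2a text argues that its timing is not affected by the intervention.

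**The case against.** The strongest reply is that the plan does not imply any particular error rate. It names six scales and no selection rule, and with six candidates the excess is at most about 1.5 points. Selecting without the arm, which the plan does not rule out, leaves no excess at all. This stands. A reader might infer that the plan's type I error is 7-10%; the documents do not support that, because the figure needs a candidate count, a criterion and an arm-in-model choice that they do not state.

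It is also fair that the plan does not say which term decides 2c. The expected cumulative effect points at least partly to arm-by-time, where no inflation was seen. The 7-10% therefore concerns the average arm difference only.

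On time-varying covariates, a reader might infer that every such adjustment is harmful. That goes too far: the plan says only that inclusion will be considered, and cancer-treatment day is on its own argument unaffected by feedback. The objection to the daily ratings remains.

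Finally, this is a pilot with a later trial planned, so the practical consequence is moderate. But 2c is a stated hypothesis with its own power calculation at a 5% alpha, and the present wording does not secure that alpha.

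**Conclusion.** The point holds in conditional form. With about 10-14 candidates screened by AIC or p-value rules with the arm in the model, the type I error of the average 2c arm difference can rise from 5% to about 7-10%. The lower end is soft: p<0.05 rules with 10 candidates gave 6.2-7.7%. It is about 5-6.5% with the six named scales alone, about 5% if selection omits the arm, and can exceed 10% with 20 or more candidates. These figures rest on 25 per arm, normally distributed candidates and complete, balanced data.

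Separately, and without a numerical size, adding daily intention, self-efficacy or affect because the arms differ can remove part of the feedback effect.

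**What to change.** For 2c:

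1. Prespecify a short fixed list of baseline covariates already in the schedule, for example cancer type, ECOG and a baseline activity measure such as the Exercise Vital Sign. Alternatively, state a selection rule and apply it with the arm term left out of the model. Either keeps the error at about 5%.
2. Do not add post-randomisation daily ratings to the main 2c model because of observed imbalance. Cancer-treatment day may stay if prespecified.
3. Put any other covariates in sensitivity models.
4. Use mean steps before the first feedback as a covariate only if there are enough such days and they are removed from the 2c outcome window. No run-in is described. With feedback each Sunday evening, those days could number from almost none to about a week, and they are also outcome days.

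The cost is a change of wording, with no new data collection. The downside is that a strongly prognostic variable outside a fixed list is used only in a sensitivity analysis.

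### The exploratory EMA moderator models state no within/between-person split, so a message-by-score coefficient need not be the day-level moderation that a timing rule would use

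*Combined protocol and SAP*

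**What the plan says.** Section 7.0, Hypothesis 2a, sets out the model that the moderator analyses reuse. On the EMA measures it says "We will include scores of the Physical Activity Intention, Physical Activity Self-Efficacy, and Affect as time-varying covariates", and on timing "we will include the scores for the day prior to the intervention so the covariates will not be affected by the intervention". The model is fitted "with participant and time as random effects and other effects as fixed". Baseline scales "will be considered as covariates as will other baseline demographic and clinical variables determined to improve the fit of the final model"; no interaction between them and the message is mentioned.

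Under Exploratory analyses the same section plans to "evaluate the moderating effects of time-varying factors measured through daily EMA" and specifies that "the moderating effect will be represented by a 3-way interaction of intervention, covariate, and time". The purpose is given as "Our ultimate goal is to be able to evaluate these factors to inform decision rules in the ultimate adaptable intervention". The plan also limits that purpose: it says that the sample size restricts power for moderators and that "formal analysis of moderating effects will only be conducted in the subsequent clinical trial".

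Neither place mentions centring at the person mean, a person-mean term or any other separation of stable level from daily deviation. Neither uses the word raw.

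**The concern.** An EMA score on a given day is the participant's usual level plus that day's departure from it. These two parts can moderate the message in different ways. Confident people may respond better to messages on every day, or a given person may respond better on days when confidence is above his or her own norm. The first says who should get messages; the second says when. Section 1.0 describes support given when an opportunity for change exists, which is mainly a question of when.

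A single unsplit score yields one coefficient for both. Nothing else in the model separates them:

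- The random participant effect absorbs differences in step level, not differences in message effect.
- The prior-day lag keeps the score free of that day's message, but yesterday's score still carries the person's usual level.
- Baseline covariates enter as main effects only.

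At stake is which moderators the pilot carries forward. A purely between-person pattern could be read as a reason for a timing rule, and a real day-level moderator could be shrunk and overlooked.

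**Working it through.** **Inputs from the documents.** 50 participants (section 3.1); 56 days with messages on 28 (section 5.4); alpha 0.05, 80% power and a detectable standardised effect of 0.109 (section 7.0, Power calculations). **Assumptions, because the documents give no figure:** EMA ICC of 0.3, 0.5 or 0.7; moderation sizes in residual SD per unit of a standardised score.

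**1. The plan's own figure.** For 2a/2b, a noncentral F test with 1 and N − 2 df and λ = N × 56 × 0.5 × 0.5 × d² gives, at N = 50, λ = 700 × 0.109² = 8.32 and power 0.807. The smallest N reaching 80% is 50. All five rows of the sample-size table reproduce (17, 50, 60, 70, 100). These are main-effect figures; the plan gives none for moderation.

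**2. What one coefficient estimates.** Write the score as Z = Zb + Zw (person level plus daily deviation), with total variance 1 and between-person share ICC. Let the message effect vary by bB·Zb + bW·Zw. Each person has both message and no-message days, so the message × Zb contrast varies within the person and the random intercept does not remove it. Fitting one message × Z term gives

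b = ICC × bB + (1 − ICC) × bW.

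**3. Numbers in.**

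| ICC | bB = 0.2, bW = 0 | bB = 0, bW = 0.2 |
|---|---|---|
| 0.3 | 0.06 | 0.14 |
| 0.5 | 0.10 | 0.10 |
| 0.7 | 0.14 | 0.06 |

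If bB = bW, then b equals both and there is no error. With bW > 0 the sign reverses only if bB/bW < −(1 − ICC)/ICC, which is −2.33, −1.00 and −0.43 at ICC 0.3, 0.5 and 0.7. For example, with bW = 0.10 and ICC 0.5, b is 0.05 if bB = 0, 0.00 if bB = −0.10 and −0.10 if bB = −0.30.

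**4. Precision.** With residual SD 1, the SE of the unsplit term is about 1/√(2,800 × 0.25) = 1/√700 = 0.038. The deviation term has only (1 − ICC) of the score variance, so its SE is about 0.038/√(1 − ICC) = 0.045, 0.053 and 0.069. Simulated values were 0.046, 0.055 and about 0.070.

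**5. Two-way term, simulated.** 50 people × 56 days, 28 message days each, main effect 0.109, person-demeaned least squares as an approximation to the random-intercept model. The split here uses the full person mean.

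| Rejection rate at ICC 0.3 / 0.5 / 0.7 | Unsplit | Deviation term |
|---|---|---|
| bB = 0.2, bW = 0 (no day-level moderation) | 37% / 73% / 93% | about 4% |
| bB = 0, bW = 0.2 | 95% / 78% / 38% | 98% / 96% / 81% |

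Repeat runs moved most of these by about 1 to 4 percentage points. A hand check at ICC 0.5 in the first row: 0.10/0.038 = 2.6 standard errors, a rejection rate of about 75%. Rates fall quickly with size. For between-person moderation of 0.1 the unsplit term rejects in 13% / 28% / 42%, and for 0.05 in 7% / 11% / 16%.

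**6. The three-way term that the plan names.** In the same scenarios, where moderation is constant over the 56 days, message × score × time averages about 0 and rejects about 5%, whether moderation is between-person or day-level. If moderation changes over time, the three-way term blends in the same way. With between-person moderation changing by 0.4 over the study and a true day-level value of 0, the unsplit three-way coefficient was about 0.11, 0.19 and 0.27 at ICC 0.3, 0.5 and 0.7. The split gave about −0.01.

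**The case against.** The strongest objection is that the rejection rates in step 5 do not belong to the planned test. The plan represents moderation by the three-way term, which in those scenarios is null and rejects at its nominal level. That stands. A reader might infer that the planned analysis would declare false moderation in 37% to 93% of trials; it would not. The rates apply to anyone who reads the two-way message-by-score coefficient. The objection also exposes a second gap: as specified, the moderation term cannot see time-constant moderation of either kind, and centring alone does not change that.

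Other points on that side:

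- **Unsplit entry is inferred.** The plan says scores and is silent on centring; it also refers to a cited methods paper that cannot be consulted here. Unsplit is the natural reading, not a stated choice. The silence still leaves two analysts free to report different coefficients.
- **The estimand is assumed.** A rule triggered by a cut-off on the observed 1-to-5 answer acts on the whole score, and for it the blended slope is the relevant average. The plan does not say which kind of rule is intended.
- **The analysis is exploratory.** The plan acknowledges limited power and defers formal moderation analysis. A reader might take the purpose statement to mean that this pilot sets decision rules; the sentence after it does not support that.
- **The assumed size is favourable.** Moderation of 0.2 is nearly twice the 0.109 main effect for which the trial is sized.

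**Conclusion.** The point holds as a gap in specification. With a single score per EMA measure, a message-by-score coefficient is an ICC-weighted blend. It equals day-level moderation only if between-person and within-person moderation are the same, and the plan gives no reason to assume so. With between-person moderation alone the two-way coefficient is 30% to 70% of that value when the true day-level value is 0; with day-level moderation alone it is shrunk to 70% to 30% of its true size (ICC 0.3 to 0.7, assumed). The same blending affects the three-way term when moderation changes over time.

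Two stronger readings are not supported. Reversal of sign is not a general consequence: it needs opposite signs and a between-person part beyond the ratios in step 3. Nor are the main effects for Hypotheses 2a and 2b biased, because messages are randomised daily, independently of the score.

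This is a cheap improvement to an exploratory analysis, with priority set accordingly.

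**What to change.** Change the exploratory moderator models only; the 2a/2b main-effect models can stay as they are.

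- Split each prior-day EMA score into the participant's running mean of earlier days and the deviation from that mean. Give each its own main effect and its own message interaction.
- Include the two-way message interactions as well as the three-way terms with time, so that time-constant moderation can be seen.
- State in advance that the deviation-by-message term informs timing rules and that the mean-by-message term describes who responds.
- If a rule based on a cut-off of the observed score is contemplated, report the unsplit coefficient alongside.

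A running mean is preferable to a first-week mean. With day-level moderation of 0.2 only, and the first week omitted, the running mean returned 0.191 to 0.197 with power 98% / 93% / 80% at ICC 0.3 / 0.5 / 0.7. A first-week mean returned 0.18 / 0.18 / 0.17 with power 98% / 88% / 70%.

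The cost is SAP wording and one extra set of interactions per moderator, with no new data. The standard error for the day-level term widens to about 0.046 to 0.070, against 0.038 for the unsplit score. The running mean is noisy in the first days, and slight attenuation remains (0.181 for a true 0.2 in the opposite-sign case).
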